# 5.2.6.2.1 AE collection

The investigator shall maintain and keep detailed records of all AEs in the participant files.

Per default SAEs/AESIs should be reported via the eCRF in the EDC system. If the EDC system is not or no longer available (e.g. after database lock), the BI paper SAE form should be used; please see Section 5.2.6.2.2.

For trial participants not rolling over to LTE trial, the following must be collected and documented on the appropriate CRF(s) by the investigator:

- From signing the informed consent onwards until the individual participant's end of trial (usually the EoS visit, please see Section 6.2.3): all AEs (serious and non-serious) and all AESIs
- After the individual participant's end of trial: the investigator does not need to actively monitor the participant for new AEs but should only report any occurrence of cancer of new histology and trial drug-related SAEs and trial drug-related AESIs of which the investigator may become aware of by any means of communication, e.g. phone call; those AEs should be reported on the BI SAE form (see Section 5.2.6.2.2), but not on the CRF

For trial participants rolling over to LTE trial the following must be collected and documented on the appropriate CRF(s) by the investigator or delegated:

# **Clinical Trial Protocol**

c40061625-02 Page 89 of 177 Proprietary confidential information © 2023 Boehringer Ingelheim International GmbH or one or more of its affiliated companies

From signing the informed consent of the parent trial onwards until the first dose of trial medication in the LTE trial: all AEs (serious and non-serious) and all AESIs.

#### 5.2.6.2.2 AE reporting to the sponsor and timelines

The investigator must report SAEs, AESIs, and non-serious AEs which are relevant for the reported SAE or AESI, on the AE or SAE eCRF pages to the sponsor's unique entry point immediately (within 24 hours of becoming aware of the event), the country specific process will be described in the ISF. The same timeline applies if follow-up information becomes available. In specific occasions, the investigator could inform the sponsor upfront via telephone in addition.

With receipt of any further information on these events, follow-up reports have to be provided. For follow-up information, the same rules and timeline apply as for initial information. All (S)AEs, including those persisting after individual participant's end of trial must be followed up until they have resolved, have been assessed as "chronic" or "stable", or no further information can be obtained. Should the EDC system not be available for more than 24 hours, reporting must occur via the BI paper SAE forms.

# For Japan:

The investigator must report medical device (prefilled syringes) failure of the trial medication that leads to AEs, SAE and/or AESI or is judged as a potential cause for leading SAEs by the investigator on the Product/Device Complaints Form to the sponsor. Please refer the instruction in ISF for further reporting requirements of medical device (prefilled syringes) failure accompanied with AEs, SAE and/or AESI or judged as a potential cause for leading SAEs.

#### 5.2.6.2.3 Pregnancy

In rare cases, pregnancy might occur in a clinical trial. Once a trial participant has been enrolled in the clinical trial and has taken trial medication, the investigator must report any drug exposure during pregnancy in a trial participant immediately (within 24 hours) by means of Part A of the Pregnancy Monitoring Form to the sponsor's unique entry point.

The outcome of the pregnancy associated with the drug exposure during pregnancy must be followed up and reported to the sponsor's unique entry point on the Pregnancy Monitoring Form for Studies (Part B).

The ISF will contain the Pregnancy Monitoring Form for Studies (Part A and B).

[figure not shown]
As pregnancy itself is not to be reported as an AE, in the absence of an accompanying SAE and/or AESI, only the Pregnancy Monitoring Form for Studies is to be completed. However, if there is an SAE and/or AESI associated with the pregnancy, it must be reported in accordance with the rules and timeline as described in Section 5.2.6.2.2.

Page 90 of 177

Proprietary confidential information © 2023 Boehringer Ingelheim International GmbH or one or more of its affiliated companies

# 5.3 DRUG CONCENTRATION MEASUREMENTS AND PHARMACOKINETICS

# **5.3.1** Assessment of pharmacokinetics

Trial participants do not have to be fasted for the PK and ADA/NAb blood sampling. Refer to the Flowchart for the time points of PK and ADA/NAb sample collection. Date and exact time of drug administration and PK and ADA/NAb sampling will be recorded on CRFs. See for reference Appendix 10.1. At study visits with study drug administration, pre-dose PK/ADA/NAb samples will be obtained approximately within 2 hours prior to start of Day 1, post-dose PK samples will also be obtained approximately 5 minutes after end of

# 5.3.2 Methods of sample collection

Handling procedures can be found in the laboratory manual in the ISF. Samples will be stored in a freezer set at the analytical laboratory until the finalisation of the clinical trial report (CTR). The study samples will be discarded after completion of the additional investigations but not later than 5 years upon the final study report has been signed.

# 5.3.2.1 Plasma sampling for pharmacokinetic analysis

For quantification of spesolimab plasma concentrations, approximately 3.0 mL of blood will be taken from a forearm vein into a K2EDTA (ethylendiaminetetraacetic acid) anticoagulant blood-drawing tube at the time points listed in the Flowchart under PK sampling. The plasma samples may be used for further methodological investigations, (e.g. stability testing) however, only data related to the analyte will be generated by these additional investigations.

# 5.3.2.2 Sampling for ADA/NAb assessment

For ADA assessment, approximately 3.0 mL of blood will be taken from a forearm vein into a K2EDTA anticoagulant blood-drawing tube at the time-points listed in the Flowchart under plasma ADA/NAb sampling. For NAb assessment, approximately 3.0 mL of blood will be taken from a forearm vein into a serum blood drawing tube at the time-points listed in the Flowchart under ADA/NAb sampling.

Page 91 of 177

**Clinical Trial Protocol** 

Proprietary confidential information © 2023 Boehringer Ingelheim International GmbH or one or more of its affiliated companies

The plasma/serum samples may be used for further methodological investigations, e.g. for further investigations to characterise ADA response or to address Health Authority questions regarding the results/methodology, however only data related to the anti-drug antibodies will be generated by these additional investigations.

# 5.3.3 Analytical determinations

Spesolimab plasma concentrations will be determined by a validated assay.

The presence of ADA to spesolimab will be assessed via a tiered approach using a validated assay (screening, confirmatory, and titration analysis, as appropriate). Time-points that are confirmed positive may be further characterised using a validated NAb assay.

# 5.3.4 Pharmacokinetic - pharmacodynamic relationship

No formal analysis of pharmacokinetic/pharmacodynamic relationships is planned. If the data suggest a pharmacokinetic/pharmacodynamic relationship of special parameters, e.g., an exploratory analysis may be performed.

Correlation between drug concentration and response may be made if adequate data are available. In addition, exploratory correlations may also be made between drug concentration and AEs.

Data may also be used to develop pharmacokinetic/pharmacodynamic models using nonlinear mixed effect modelling techniques, if feasible. For this purpose, data may also be combined with data from other trials. Modelling activities will be planned and documented separately according to internal and external guidelines and Standard Operating Procedures (SOP).

# 5.4 ASSESSMENT OF BIOMARKERS

This section refers to exploratory biomarkers. Established biomarkers of efficacy and safety are described and discussed in Section 5.1 and Section 5.2.

The further objectives, related to exploratory biomarkers, are specified in Section 2.2.1.

Page 92 of 177

Proprietary confidential information © 2023 Boehringer Ingelheim International GmbH or one or more of its affiliated companies

5.4.1	Biochemical and cellular biomarkers
5.4.3	Imaging biomarkers
5.4.4	Methods of sample collection
	nstructions on sampling, preparation, processing, shipment, and storage of samples led in the laboratory manual in ISF. For sampling time-points, refer to the
For the as	ood for gene expression analysis sessment of RNA expression, whole blood will be collected from a forearm vein according to standard procedure provided in ISF.
For the sk	sy and US lesion evaluation in biopsies, one punch biopsy from lesional skin will be collected at Visit 2 and Visit 10 An additional paired non-lesional skin biopsy will also be at baseline.

Page 93 of 177

Proprietary confidential information © 2023 Boehringer Ingelheim International GmbH or one or more of its affiliated companies

# Selected trial sites with US capability

At selected trial sites with US capability, skin biopsies (lesional and non-lesional) will be obtained as mandatory. Skin biopsies will be done under US guidance to ensure optimal skin biopsy selection and increase the quality of sampling.

# All other trial sites (i.e. other than selected trial sites)

Skin biopsies (lesional and non-lesional) and US lesion evaluation with US imaging will be optional.

# Study samples

The study samples will be discarded after completion of any investigations, but not later than 2 years after the biomarker report has been signed. Any leftover samples or derived material from pre-specified analyses (e.g. RNA, DNA, and blood) may be used for method development/validation but will be destroyed no later than 2 years after the biomarker report has been signed. Exceptions are remainders of study samples for which a participant has voluntarily accepted a biobanking option and has provided a signed ICF (see Section 5.5).

# 5.4.5 Analytical determinations

Serum, whole blood and skin biomarkers will be analysed using established parameters for each analyte and the corresponding matrix.

Characteristics of the analytical methods for the analysis of the biomarkers will be given in detail in an accompanying technical/biomarker report.

The biomarker assay analysis of all biomarker samples will be performed in a staged approach. The initial analysis will focus on selected time-points, and depending on these results, a decision will be made about further analysis of all samples. This is due to the

Page 94 of 177

Proprietary confidential information © 2023 Boehringer Ingelheim International GmbH or one or more of its affiliated companies

exploratory nature of the mechanism being tested and the timing of effect on candidate biomarkers in the study. And this approach may also imply that not all collected samples will be analysed, especially in case of termination of the project/trial.

# 5.5 BIOBANKING

Participation in biobanking is voluntary and not a prerequisite for participation in the trial. Biobanking will only occur after a separate biobanking informed consent has been given in accordance with local ethical and regulatory requirements.

Unspecified DNA banking:

An additional blood sample for DNA banking will be collected in at Visit 2 (see Flowchart).

## 5.6 OTHER ASSESSMENTS

# **Assessments PROs**

Administration of paper or electronic PRO (PRO/ePRO) assessments will be in accordance with the guidance from regulatory authorities and international societies (e.g. ISPOR). Trial participants are required to fill PRO/ePRO assessments on their own in a quiet area/room at the frequency as specified in the CTP, without being influenced by the investigator or other members of the trial team. The PRO/ePRO assessments are to be completed by the participant without any help from or interpretation/translation by other people. If this is not possible, the PRO/ePRO assessments are not to be done.

The completion of PRO/ePRO assessment by the participant and the mode of administration will be documented.

# Photo images

Photographs of trial participant's skin affected areas are collected to document clinical condition during the clinical trial, i.e. before and during the treatment. Photo images will be mandatory at selected sites who will also be collecting skin biopsies and US images for lesion evaluation. All trial participants in the selected sites must accept photoimaging. For all other sites, photoimaging will be optional. An informed consent on photoimaging and related signature must be obtained from the concerned trial participants. Trial participants accepting the photoimaging to be taken must sign an informed consent.

Trial participants who consent will have photographs taken at the designated study visits listed in the Flowchart.

The skin photo images will be obtained using a standardised software and supplied to the trial site by a digital imaging vendor. The photographs taken using this software are automatically

Boehringer Ingelheim BI Trial No.: 1368-0098

c40061625-02 Clinical Trial Protocol Page 95 of 177

Proprietary confidential information © 2023 Boehringer Ingelheim International GmbH or one or more of its affiliated companies

uploaded to the vendor's central secured server using an encrypted data transfer and anonymous subject allocation. Training and detailed instructions will be provided by the imaging vendor.

# 5.7 APPROPRIATENESS OF MEASUREMENTS

All methods used in this trial are standard methods.

Page 96 of 177

Proprietary confidential information © 2023 Boehringer Ingelheim International GmbH or one or more of its affiliated companies

# 6. INVESTIGATIONAL PLAN

The trial will be conducted worldwide as multinational trial at multiple sites experienced in the management of dermatologic diseases, including dermatological conditions such as HS.

The regions and clinical sites will be selected based on the availability of patients with HS and their experience in conduct of clinical trials and use of the clinical assessments.

Part 2 investigational plan will be detailed in an amendment based on Part 1 safety and efficacy available data at the time of Part 1 primary analysis. The following text of this section applies to Part 1 of the study described in this protocol.

All trial participants are to adhere to the visit schedule as specified in the Flowchart. Each visit date (With its window) up to EoT is to be counted from Visit 2 at Day 1 (first trial drug administration day). If any of these visits have to be rescheduled, the date of subsequent visit should be calculated from Day 1.

For trial 1	participants not rolling over to LTE trial, FUP refers to Follow-up visit which will be
scheduled	after last study drug administration. EoT refers to the End of Treatment
visit at	(or earlier if a trial participant terminates study drug before

EoS refers to End of Study visit which will be scheduled after last study drug administration (after REP period). It is considered to be the safety follow-up and it should happen 112 days after the last drug administration or 98 days after the EoT visit.

For trial participants rolling over to LTE trial, EoT and EoS dates will be the same. These patients will not undergo the safety follow-up period because they will be followed in the LTE trial. For these trial participants EoT visit of this trial and first visit of the LTE trial should occur the same day.

Additional visits for the purpose of re-testing of laboratory parameters or AE monitoring may be included as deemed necessary by the investigator.

In the event of force majeure or other disruptive circumstances (e.g., pandemic, war) the execution of the investigational plan as per this clinical trial protocol may not be feasible. With the consent of the participant, the sponsor and investigator may agree on alternative, back-up or rescue methodology which may include virtual trial participant visits and assessments, home healthcare nurse visits, or bio-sample pick up from the participant's home. The implementation of these measures will depend on participant's consent, operational feasibility, local law and regulations. If alternative methodology is implemented, the deviations from the original plan will be precisely documented.

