## **FLOWCHART**

c40061625-02

Part 1 (Phase IIb): Flowchart will be consolidated for Part 2 (Phase III) based on the primary analyses and/or interim analyses of Part 1. (cont.)

Trial Periods			Treatment 1	Period – afte	r u	p to			ЕоТ	Safety Follow-Up
Visit	24*	25	26*	27	28*	29	30*	31	EoT 	EoS
Day										or 98 days from EoT.
Time window for visits (days)	±3	±3	±3	±3	±3	±3	±3	±3	±3	+7
All adverse events 	X	X	X	X	X	X	X	X	X	X
Concomitant therapy	X	X	X	X	X	X	X	X	X	X
Completion of patient participation										X

HiSCR: Hidradenitis Suppurativa Clinical Response, IHS4: International Hidradenitis Suppurativa Severity Score System, HASI: Hidradenitis Suppurativa Area Severity Index, HS-PGA: Hidradenitis Suppurativa Physician's Global Assessment, DLQI: Dermatology Life Quality Index, HiS-QoL: Hidradenitis Suppurativa Quality of Life, PGI-C: Patient Global Assessment of Change, PGI-S: Patient Global Assessment of Severity, HODS: Hidradenitis odour and drainage scale, HADS: Hospital Anxiety and Depression Scale, C-SSRS: Columbia-Suicide Severity rating Scale, IHS4: International Hidradenitis Suppurativa Severity Score System

- \* Visits should happen at site. However, for Visits 7, 9, 15, 20, 22, 24, 26, 28, and 30, trial participants will be offered the possibility to have home nursing visits if locally allowed. In exceptional circumstances (i.e. pandemic, conflict, other), visits might take place by phone just to collect safety information.
- Day of randomisation/day of first intake of randomized medication. If needed, some Visit 2 assessments may be conducted within 2 days before or after the actual visit date after consultation with the sponsor.

9

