- Infection testing: at screening and at EoT visit. See Section of safety laboratory parameters for complete list of testing required (see Table 5.2.3: 2). For Japan only, if there is no chest X-ray test or CT taken within 3 months prior to Visit 1, it should be taken at screening visit. For South Africa only, tuberculosis infection testing should be done approximately at 6 months intervals. For this reason, participants from South Africa QuantiFERON testing should be done at visit 19.
- ECG measurements should always precede blood sampling and drug administration. The ECG measurements need to be conducted at timepoints indicated in the Flowchart. Additional ECG measurements may be performed if the investigator deems it clinically indicated.
- Trial participants who terminate study drug early should do the EoT visit as soon as possible. These participants will then do EoS visits, after last study drug administration. When this discontinuation happens before Visit 14 participants ideally should also continue visits for assessments of efficacy until as per Flowchart.
- Desoxyribonucleic Acid (DNA) banking sample is optional. This sampling is only possible if the trial participant agreed by signing a separate informed consent. For details, please see Section 5.5.
- Skin biopsy is mandatory at selected sites and should be sampled under ultrasound (US) guidance. For all other sites it is optional. Sites without the US required capabilities cannot perform skin biopsies. See Section 5.4.4.
- 13 US lesion evaluation is mandatory at selected sites with US capabilities. For all other sites it is optional. See Section 5.4.3.
- 14 IHS4 is used to classify trial participant's severity at baseline. IHS4 will be derived from lesions count by a trained health care professional
- Trial participant diaries will be handed to trial participants with the objective to collect daily information about NRS Pain and Pruritus from baseline, after being trained, till Visit 19 After Visit 19, NRS pain and NRS pruritus will be collected on a daily basis during the 7 days prior to the next scheduled visit (prior to Visit 23, Visit 27, Visit 31, and EoT visit). Site staff will collect the diaries from trial participants at visits indicated in the Flowchart to assess pain and pruritus since last visit. See Section 5.1.1.
- 16 At Screening, the C-SSRS baseline/screening scale will be completed. At all subsequent visits the "since last visit" scale will be completed.

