## Residual Effect Period (REP)

The REP of spesolimab is 16 weeks. This is the period after the last dose with measurable drug levels and/or pharmacodynamic effects still likely to be present.

c40061625-02 Clinical Trial Protocol

Page 28 of 177

Proprietary confidential information © 2023 Boehringer Ingelheim International GmbH or one or more of its affiliated companies

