In case the infusion of study drug is permanently discontinued before the whole amount of the prepared solution has been administered to the trial participant, every effort should be made to complete all remaining study assessments of the visit.

Trial participants who discontinue treatment permanently and prematurely prior to the planned EoT visit should be registered as discontinued from treatment in IRT. These participants should follow the scheduled visits as much as possible as defined in the Flowchart: the EoT visit procedures should be conducted either immediately or as soon as

c40061625-02

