7.8.1 Adverse Events

Date: 07-08-2024, Version 1.0

Unless otherwise specified, the analyses of AEs will be descriptive in nature, which will include all on-treatment events up to week 8, week 16 treatment, as well as all events during the whole on-treatment period respectively. All analyses of AEs will be based on the number of subjects with AEs and NOT on the number of AEs.

AEs will be coded with the most recent version of MedDRA®. Patients will be analyzed according to the actual treatment received.

The analysis of AEs will be based on the concept of treatment emergent adverse events (TEAE). That means that all AEs occurring between first drug intake till 112 days after last drug intake will be assigned to the on-treatment period. All AEs occurring before first drug intake will be assigned to 'screening' and all AEs occurring after last drug intake + 112 days will be assigned to 'follow-up' (for listings only). For details on the treatment definition, see Table 6.1:1.

The exposure adjusted incidence rate (per 100 patient years) of a selected treatment emergent adverse event is defined as the number of patients experiencing the adverse event per

Proprietary confidential information © 2024 Boehringer Ingelheim International GmbH or one or more of its affiliated companies.

treatment group during time at risk divided by the total time of patients at risk in that treatment group to contribute the event to the analysis multiplied by 100 (per 100 patient years).

Time at risk [patient years] = (date of onset of AE– first treatment start date within that treatment period + 1) / 365.25

If, for a patient, the selected treatment emergent adverse event didn't occur during the above defined treatment period (per Table 6.1:1) then the time at risk will be censored at the earliest of date of death, last contact date per EoS page, or the end of the above defined treatment period.

For each selected treatment emergent AE, the exposure adjusted incidence rate will be calculated as:

Incidence rate [1/100 Patient years (pt-yrs)] = 100 * number of patients with TEAE / Total TEAE-specific time at risk [patient years].

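### For participants who do not roll over to the LTE trial, the two End of Study anchors agree only if EoT is exactly 14 days after the last dose; with a shorter gap, one of them permits EoS inside the protocol's own 16-week residual effect period.

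*Protocol*

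**What the plan says.** **Length of the REP.** Protocol Section 1.2: "The REP of spesolimab is 16 weeks".

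**Timing of EoS.** Protocol Section 6 gives the intent: "EoS refers to End of Study visit which will be scheduled after last study drug administration (after REP period"). Its next sentence gives the rule: "it should happen 112 days after the last drug administration or 98 days after the EoT visit". The Flowchart EoS column repeats the second anchor, "or 98 days from EoT". Flowchart footnote 2 and Section 6.2.3 also offer a choice between last intake and EoT, with the intervals blacked out. The Flowchart window is +7 days for EoS, with no minus side, and ±3 days for Visit 31 and for EoT.

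**Early discontinuers, EoT.** The Flowchart footnotes say "Trial participants who terminate study drug early should do the EoT visit as soon as possible". Section 3.3.4.1 says "the EoT visit procedures should be conducted either immediately or as soon as" possible. Section 3.1 has EoT replace the next planned visit.

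**Early discontinuers, follow-up.** The Flowchart footnote on early termination and Sections 3.3.4 and 3.3.4.1 tie follow-up to the last drug administration only. Section 3.3.4.1 also asks sites to try to keep these participants under observation for a minimum time (blacked out) after the last dose.

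**Adverse events.** For participants not rolling over, Section 5.2.6.2.1 has all AEs collected until the individual's end of trial, usually EoS. Section 7.2.6 counts events as treatment-emergent to the end of the REP. SAP Section 7.8.1 puts this in days: "all AEs occurring between first drug intake till 112 days after last drug intake will be assigned to the on-treatment period".

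**The concern.** The intent in Section 6 and the rule that follows it are not equivalent. The intent is tied to the last dose through the REP. The rule adds an alternative tied to EoT, and nothing says which date prevails. A site that books EoS 98 days after an early EoT complies with Section 6 and the Flowchart, yet may close the participant's follow-up before the REP is over.

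At stake is safety ascertainment. The analysis window for treatment-emergent events is fixed at 112 days after the last dose, but active collection can stop before then. The participants most exposed are those who stopped treatment early, including those who stopped because of an adverse event. Sites also face two sets of instructions for this group: Flowchart footnote 2 offers the EoT anchor in the same note that asks for an early EoT, while other passages use the last dose alone.

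**Working it through.** **Inputs.** REP of 16 weeks (Protocol Section 1.2). Anchors of 112 days from last dose or 98 days from EoT (Section 6). EoS window of +7 days, and ±3 days for Visit 31 and EoT (Flowchart). Let g be the days from last dose to EoT.

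**The plan's own figure.** 16 × 7 = 112 days, so the last-dose anchor equals the REP exactly.

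**Where the anchors agree.** g + 98 = 112 gives g = 14, and no other value.

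**Shortfall under the EoT anchor.** EoS opens at day g + 98 after the last dose and its window closes at day g + 105. The shortfall against the REP is max(0, 14 − g) at opening and max(0, 7 − g) at closing.

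| g | EoS opens (day) | Short by | Window closes (day) | Short by |
|---|---|---|---|---|
| 0 | 98 | 14 | 105 | 7 |
| 3 | 101 | 11 | 108 | 4 |
| 7 | 105 | 7 | 112 | 0 |
| 8 | 106 | 6 | 113 | 0 |
| 11 | 109 | 3 | 116 | 0 |
| 14 | 112 | 0 | 119 | 0 |

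The maximum is 14 of 112 days (12.5% of the REP). If g is below 7, even the last day of the EoS window falls before day 112.

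**Which gaps are plausible for early discontinuers?** An immediate EoT can give any small g. If EoT replaces the next planned visit, g depends on visit spacing. Visit 10 is Week 8 (SAP Section 7.4.1) and Visit 14 is Week 16 (SAP Section 6.1). From Visit 2 to Visit 10 there are 8 intervals in 8 weeks, about 7 days each. From Visit 10 to Visit 14 there are 4 intervals in 8 weeks, about 14 days each. On this route g is about 7 up to Week 8, and about 14, with little or no shortfall, from Week 8 to Week 16. Later spacing is blacked out.

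**Completers.** The nominal Visit 31-to-EoT gap is blacked out. If it is 14 days, an assumption suggested by 112 − 98, then Visit 31 at +3 and EoT at −3 give g = 14 − 6 = 8. EoS may then fall at day 106, 6 days short. The in-window range under this assumption is g = 8 to 20; there is no shortfall from g = 14 upward.

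**Effect on the safety tables.** SAP Table 6.1:1 ends the on-treatment period at the earliest of several dates, including last dose + 112 days for early discontinuers and the last contact date. SAP Section 7.8.1 censors time at risk at last contact, so the exposure-adjusted rates do not count unobserved days. The tables of numbers of patients with AEs in the same section make no such adjustment.

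**The case against.** The strongest reply is that the protocol does not plan a short follow-up. Section 6 itself places EoS after the REP, and the passages specific to early discontinuers use the last dose, not 98 days from EoT. A reader might infer from the 98-day alternative that early stoppers are meant to leave at day 98. The documents do not support that. What stands is a conflict: Section 6, the Flowchart column and footnote 2 still offer the EoT anchor, and the last-dose passages do not withdraw it.

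Four further limits are fair:

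- **Scope.** Participants rolling over to the LTE trial have no safety follow-up period here and are unaffected.
- **Continued visits.** Those stopping before Visit 14 are ideally to continue efficacy visits to Visit 14. Week 16 is 112 days after Day 1, so someone whose last dose was within 14 days of Day 1 would be seen to day 98 after that dose or beyond. This is not mandatory and does not help later stoppers.
- **Not all information is lost.** A reader might infer that nothing is captured after EoS. In fact new cancers and drug-related SAEs and AESIs that come to the investigator's attention are still reported, though not on the CRF (Section 5.2.6.2.1). Ongoing events are followed (Section 5.2.6.2.2), and extra safety visits are possible (Section 6.2.3). The loss is in active ascertainment of new events.
- **Censoring.** The exposure-adjusted rates handle short follow-up; the tables of patients with events do not.

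**Conclusion.** The inconsistency is real and limited in size. For participants not rolling over, the rule permits EoS up to 14 days before the 112-day REP ends whenever EoT comes less than 14 days after the last dose. This arithmetic needs no assumption beyond the stated 112, 98 and 16 weeks. That early discontinuers will often have short gaps follows from the instruction to hold EoT as soon as possible; how many will be affected cannot be known from the documents. The completer case (day 106) rests on an assumed 14-day nominal gap. The consequence is a possible loss of active collection of new events at the end of the treatment-emergent window, reflected in the tables of patients with AEs. It should be corrected as wording that contradicts the protocol's own figure. No efficacy analysis, sample size or error rate is touched.

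**What to change.** Reconcile Protocol Section 6, the Flowchart EoS column, Flowchart footnote 2 and Section 6.2.3 with three things:

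- the 16-week REP in Section 1.2;
- the last-dose anchoring for early discontinuers in the Flowchart footnote on early termination and Sections 3.3.4 and 3.3.4.1;
- the treatment-emergent window in Protocol Section 7.2.6 and SAP Section 7.8.1.

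After the change, the stated EoS timing and the REP-based window should agree, and a site should be able to tell which date governs when the anchors differ. The rule itself is for the sponsor to decide.

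The cost is a small wording change in a few places and no added visit. EoS may move later for some participants, by an amount that depends on the rule chosen.
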